- Participants will be fully informed about the study during the informed consent process and instructed to decline to answer any question or to discuss any issues they find troubling. If the interviewer feels that the participant is becoming anxious or fearful over a question, the interviewer will move on to the next question and document the reasoning.
- We will provide a letter with the principal investigator's and research assistant's names and phone numbers and instructions to call with questions or concerns.
- If a participant expresses significant distress (e.g., suicidal ideation) at any point during the study, Drs. [name] or [name] (both clinical psychologists) will assess the participant and make an appropriate referral for clinical care if needed. In addition, for distressed patients, [name] or another study team member will contact the referring oncologist to inform them of the patient's high level of distress. Patients will also be encouraged to contact the healthcare team if they experience moderate to severe symptoms.

Suicidality Risk Protocol

If a participant expresses suicidal ideation, our research team will use an evidence-based algorithm that was developed in 4 earlier depression effectiveness trials in medical patients⁷⁴⁻⁷⁷ and was tested in two recent trials in general medical (SCAMP trial)⁷⁸ and cancer (INCPAD trial)⁶⁰ patients. Evidence supports the utility of this algorithm (Appendix Q).⁷⁹ By this algorithm, participants are classified as minimal, lower, or higher risk. Participants with higher risk of suicide according to this algorithm will be considered for emergency detention. The latter constitute <2% of participants enrolled in depression trials, and we have a protocol for expedited evaluation by a clinical psychologist for the rare participant in the higher risk group, also tested in the SCAMP and INCPAD trials. All research personnel will be trained by the PI in this protocol. Specifically, after asking follow-up questions (see Appendix Q), [name] or [name] (both clinical psychologists) will review the information the same day to determine the

appropriate course of action. If they believe that the participant is in immediate danger of harm, they will report it, potentially to authorities including the police. If the participant is not receiving mental health services, then they will be referred to mental health services at a location convenient to them.

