While some patients will be approached in clinic as outlined above, other patients will be approached via a mailing and phone calls. Before sending a study introductory mailing to any potentially eligible patients, the project coordinator will discuss with the oncologist co-investigator if these potentially eligible patients may receive information about the study. An introductory letter signed by the patient's oncologist and the PI will be sent to notify each potentially eligible person about the study (see Appendix C). The recruitment brochure (Appendix A), consent form, and authorization form will also be included in the initial mailing with the introductory letter. Any interested patients will be invited to call for more details. The letter also will have an "opt out" component; thus, patients who are not interested in the study may call or email the research assistant to indicate that they do not wish to be contacted further.

A research assistant will call all prospective participants who do not opt out within approximately 1 to 2 weeks after the letter is mailed. The research assistant will describe the study, review the consent and authorization forms, and ask if they would like to participate (see Appendix D for telephone script). During that initial call, interested patients will complete the screening assessment described above (see Appendix B—screening questionnaires). The research assistant will read the items and response choices aloud and patients will select response options. Those who are interested and eligible will provide verbal consent for study participation and verbal authorization to collect information from medical records. Verbal consent was chosen in place of written informed consent to minimize the number of documents that link the participant with the research and therefore reduce the risk of a breach of confidentiality. In addition, the entire study will be conducted via the phone. Thus, we do not have the opportunity to obtain written consent during a face-to-face meeting with the patient. If a potential participant does not answer the phone, a brief voicemail will be left only once (see Appendix D for telephone script), and we will only speak with the potential research participant up to 5 times within approximately 1 to 4 weeks after the first phone call.

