Advanced patients and caregivers ($N = 50$ dyads) who are eligible and provide informed consent will complete individual phone assessments at baseline and approximately 2 weeks and 3 months following the final intervention session (see Table 1 in section 5.0 above for allowable assessment windows). The baseline assessment takes about 30 minutes for patients and 25 minutes for caregivers. Each follow-up assessment takes about 25 minutes for patients and 20 minutes for caregivers. Interviewers will be blind to study condition. Assessments will include questions regarding demographics, medical history, and primary and secondary outcomes. Participants will be provided with copies of response options via email or postal mail to facilitate survey completion (see Appendix E). Patients and caregivers in the ACT condition will also be invited to complete a 30-minute individual qualitative interview about intervention acceptability within approximately two weeks of the 2-week follow-up assessment. Each participant will receive \$40 in Target gift cards via postal mail for each completed assessment (baseline and 2-week and 3-month follow-ups) for a possible total of \$120 in gift cards (\$160 in gift cards for ACT participants only) for their time. There is no cost to study participants. If we cannot reach

a participant for an interview or phone session after several attempts, we will mail them a letter asking them to contact the study team (Appendix C). Table 2 below outlines the assessment schedule at baseline and the two follow-ups.

Table 2. Quantitative Measures						
Domain	Measure	# Items	Baseline	2-week follow-up	3-month follow-up	Administered to Patients (P) or Caregivers (C)
Sociodemographics	Sociodemographics	7-8	X			P, C
Medical comorbidity	Checklist of 8-9 conditions	8-9	X			P, C
Functional status	Patient-reported ECOG	1	X	X	X	P
Cancer information (e.g., date of diagnosis, cancer treatments)	Chart review	n/a	X	X	X	N/A
Intervention acceptability	Intervention acceptability scale	6		X		P, C
Primary patient outcome: fatigue interference	Fatigue interference subscale of FSI	7	X	X	X	P
Primary caregiver outcome: caregiving burden	12-item short-form of Zarit Burden Interview	12	X	X	X	C
Secondary outcomes:						
• Sleep interference	PROMIS short-form sleep-related impairment measure	8	X	X	X	P
• Engagement in daily activities	PROMIS short-form measure of ability to participate in social roles and activities	6	X	X	X	P, C

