• Progress in value-based living	Progress subscale of the Valuing Questionnaire	5	X	X	X	P, C
• Psychological flexibility	Acceptance and Action Questionnaire-II	7	X	X	X	P, C
• QoL	McGill Quality of Life Questionnaire-Revised (patients) or PROMIS global health measure (caregivers)	15 or 10	X	X	X	P, C
Tertiary outcomes:						
Physical and mental healthcare use	Healthcare use interview	7-8	X	X	X	P, C
Medications	Medication interview	n/a	X	X	X	P, C
Severity of symptoms:						
Fatigue severity, sleep disturbance, anxiety, depressive symptoms, pain, and cognitive symptoms	Fatigue severity and frequency items from the FSI; PROMIS short-form measures of sleep disturbance, anxiety, depression, pain, and cognitive function	30 or 37	X	X	X	P, C (except that pain is only assessed in patients)

ECOG = Eastern Cooperative Oncology Group; FSI = Fatigue Symptom Inventory; PROMIS = Patient-Reported Outcomes Measurement Information System; QoL = quality of life.

Study Measures

Advanced GI cancer patients and caregivers will each complete a 5-minute screening assessment to determine eligibility using the measures described below (see Appendix B).

Screening measures: Patients will first complete a validated 6-item cognitive screener.⁴⁷ Patients with 3 or more errors on this measure will be ineligible for this study. Then patients will complete the 1-item Patient Generated Subjective Global Assessment (PG-SGA; the patient-reported version of the Eastern Cooperative Oncology Group score).^{48, 50} Those with a score above 2 will be excluded from the study. Next, patients will complete the 7-item Fatigue Interference subscale of the FSI.^{36, 37} Eligible patients will have a mean score ≥ 2.5 , indicating moderate to severe fatigue interference. All measures have well-established reliability and validity and have been studied in cancer populations. Caregivers will complete the 6-item Zarit Burden Interview³⁹ and the 4-item PROMIS anxiety and depression measures.⁴⁹ Eligible caregivers will have a Zarit Burden Interview score of 6 or higher or a PROMIS anxiety or depression T-score of 60 or higher (at least one standard deviation above the population mean).

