Tertiary outcomes. Patients and caregivers will report their physical and mental healthcare use in five domains (e.g., ER visits, outpatient visits) in the past 3 months at baseline and over the study period.^{59, 60} These reports of healthcare use were sensitive to change in an R01-funded cancer trial.⁶¹ At all time points, participants will also report whether professionals referred them to support services and whether referred services were received.^{52, 62} At all time points, participants will also report current medications using established methods from prior trials.^{63, 64} We will compute the total number of medications at each time point, as this variable had strong predictive validity for both healthcare use and costs in older adults over a 1-year period.⁶⁵

Measures of symptom severity. Symptom severity will be assessed to characterize the sample. For both patients and caregivers, fatigue severity and frequency will be measured with six items from the FSI,^{36, 37} and sleep disturbance, cognitive symptoms, anxiety, and depressive symptoms will each be assessed with an 6-item PROMIS measure.^{40, 41, 49, 57, 58, 66} Patients will also complete 3-item and 4-item PROMIS measures of pain severity and impact on functioning, respectively.⁵⁸

ACT Intervention Procedures

Drs. [name] and [name] developed the ACT manual (see Table 3 and Appendix K), which was informed by literature on the experiences of advanced GI cancer patients and caregivers,^{2, 3, 15, 67, 68} the ACT model,^{24, 35} previous ACT trials with cancer patients and other populations with physical and mental health conditions,^{25, 26, 29, 31, 33, 34} and [name] extensive experience delivering ACT to cancer patients and caregivers. A licensed therapist will deliver the intervention. While the therapist will aim to hold sessions on a weekly basis for 6 weeks, participants will have up to 12 weeks to complete the 6 sessions. Patients and caregivers will complete sessions 1 and 4-6 together via speakerphone. Sessions 2 and 3 will be delivered to patients and caregivers separately. Holding both dyadic and individual sessions will allow the therapist to meet the shared and unique needs of patients and caregivers. We adapted ACT to the dyad by incorporating joint mindfulness practices and leveraging the relationship during discussions. For example, participants will discuss moments of emotional connection with each

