10.0 Study Withdrawal/Discontinuation

Criteria for removal from the study are as follows:

- Observed severe cognitive impairment that renders continued participation in the study impossible, such as confusion or impaired ability to read or to provide accurate answers to the interviewer.
- The patient consents to participate in the study, but their family caregiver declines study participation or is not eligible for this study. The patient would no longer be eligible to participate in this study, as we are interested in examining data from patient-caregiver dyads.
- If the patient or caregiver is no longer able to participate in this study due to death or medical factors or decides to stop participation, then the other member of the dyad (patient or caregiver) will no longer be eligible to participate in this study.
- The participant expresses significant distress related to completion of the study (the PI will refer the participant to clinical services if needed).
- The participant provides verbal or written notification that she has decided to discontinue study participation.
- The participant does not follow the study rules (e.g., repeatedly does not answer the phone to complete a scheduled interview).
- Any other reason for which the principal investigator believes the participant should be withdrawn.

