Aim 2. Given that this is a pilot study, our data analytic approach for Aim #2 will be to derive effect size estimates rather than test for statistical significance. A linear mixed-model repeated measures approach (SAS Proc-Mixed) will be used to examine ACT's effects on primary and secondary outcomes. For outcome measures that only patients or caregivers complete (e.g., patient fatigue interference or caregiver burden), models will include main effects of time (as categorical) and study group and the time-by-study group interaction. Treatment effects will be evidenced by the interaction between time and study group (i.e., group mean differences after the intervention but no such differences at baseline). Models will include random intercepts to account for nonindependence of individuals' scores across time. For outcomes reported by patients and caregivers (e.g., psychological flexibility), multilevel modeling for dyadic data will be used.^{83, 84} Models will include the main effects of time, study group, and social role (patient vs. caregiver) as well as all two and three-way interactions between these variables. The time x study group x role interaction will estimate the degree to which treatment effects are different for patients and caregivers. Dyadic models will include random intercepts for patients and caregivers, as well as the covariance between the intercepts to account for nonindependence across time and across partners.

Aim 3. To conduct data analyses for Aim #3, we will use logistic and Poisson regression models to explore the effects of ACT on patient and caregiver physical and mental health service use (e.g., number of patient ER visits, patient and caregiver use of counseling and/or psychiatric medication). Logistic and Poisson regression analyses are appropriate for binary and count outcome data, respectively. Analyses will examine study condition as a predictor of health service use over the entire study period, controlling for baseline service use. Support service referrals will be a covariate in analyses of mental health service use.

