12.0 Statistical Data Management

Primary data will be collected via phone interviews and stored electronically in passphrase protected files on the secure Psychology network drive accessed through an encrypted computer. Only IRB-approved members of the research team will have access to study files. The storage location will be backed up automatically every day. Paper files will be stored in a locked filing cabinet in a locked room in the PI's laboratory. Other data sources include data from medical records that will be stored in separate passphrase protected electronic files and merged with the primary data as needed. Quality assurance steps will include built in range checks. The following quality control methods will be used: 1) single data entry with two independent checks of the accuracy of every data point; and 2) discussion of any data entry questions with the PI.

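### Aim 3 wants patient service use over the whole study, but its only named source is an interview that stops when the patient dies, falls too ill, withdraws or loses the caregiver; adding ER dates to the scheduled chart reviews would be a cheap cross-check

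*Combined protocol and SAP*

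**What the plan says.** Section 7.0 (Tertiary outcomes) sets the measurement: "Patients and caregivers will report their physical and mental healthcare use in five domains". It names only ER and outpatient visits as examples of the five. Table 2 lists the instrument as a "Healthcare use interview" at baseline, 2 weeks and 3 months, for patients and caregivers.

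Section 11.0 (Aim 3) gives the analysis, by logistic and Poisson regression: "Analyses will examine study condition as a predictor of health service use over the entire study period, controlling for baseline service use". Its first example is the number of patient ER visits. It states no time-at-risk term and no rule for death. Missing data in general are to be multiply imputed with 50 samples.

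Section 10.0 ends participation for anyone who is "no longer able to participate in this study due to death or medical factors or decides to stop participation", and the other member of the dyad then becomes ineligible too. Repeatedly unanswered interview calls are also grounds for removal.

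Table 2 also schedules chart review for patients at the same three time points, under the entry "Cancer information (e.g., date of diagnosis, cancer treatments"). Patients recruited by mail and phone give "verbal authorization to collect information from medical records", and those met in clinic receive an authorization form. Section 12.0 provides for "data from medical records that will be stored in separate passphrase protected electronic files and merged with the primary data as needed".

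**The concern.** The outcome is defined over a fixed period, but its source runs only as long as the patient can be interviewed. Whatever happens after the last completed interview is not observed, and a patient lost before the 2-week visit contributes no follow-up use at all.

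The loss is unlikely to be unrelated to use. Patients have unresectable stage III or stage IV disease (section 4.1), and section 10.0 lists death and medical factors as reasons for leaving. Section 1.0 reports that all attrition in an ACT trial in late-stage ovarian cancer was due to death or starting hospice.

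A time-at-risk offset would correct for shorter observation but would not recover unseen events that occur at a different rate. Multiple imputation would fill the gap from patients well enough to be interviewed. At stake is how far the Aim 3 estimate for patient ER use describes everyone randomised, in a pilot meant to inform a larger trial.

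**Working it through.** **The plan's own figures.** None is given for service use. The only related figure is the power statement in section 11.0: 34 patients, d = 0.99, two-sided 0.05, 80% power. With 17 per arm a noncentral t calculation gives 79.9%, so it reproduces. It does not bear on Aim 3 but supplies two of the loss rates below.

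**Inputs**
- Interview times: first session about 1 week after baseline, sixth session 5 weeks later. The interviews then fall at 1 + 5 + 2 = week 8 and 1 + 5 + 13 = week 19 (section 5.0, target dates). The intervals are 8 and 11 weeks.
- Loss by the 2-week visit: a1 = 0.15 (section 11.0).
- Loss by 3 months: a2 = 0.21, from 79% retention at 12 weeks in the team's metastatic breast cancer pilot (section 1.0). As a less favourable case, a2 = 0.32, because 34 of 50 is 68%. The plan attaches the 34 to the 2-week visit; using it at 3 months is my assumption.
- Use rate of lost patients relative to others: k = 2, 3, 4 (assumption; the documents give none).
- Once lost, a patient is taken to give no later interview.

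**Patients interviewed.** 50 × 0.85 = 42.5 at 2 weeks; 50 × 0.79 = 39.5, or 50 × 0.68 = 34, at 3 months.

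**Case A: lost patients remain at risk to week 19** (withdrawal, illness without death, caregiver leaves).

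Coverage of patient time = [8(1 − a1) + 11(1 − a2)] / 19.
- a2 = 0.21: (6.80 + 8.69) / 19 = 0.815
- a2 = 0.32: (6.80 + 7.48) / 19 = 0.752

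Share of visits captured = [(1 − a2) + (a2 − a1)·k·8/19] / [(1 − a2) + a2·k]. For k = 2 and a2 = 0.21: (0.79 + 0.0505) / (0.79 + 0.42) = 0.695.

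**Case B: risk ends midway through the missed interval** (as with death). Patients lost early have 4 unseen weeks; those lost later have 8 seen and 5.5 unseen.

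Coverage = seen / (seen + unseen).
- a2 = 0.21: 15.49 / (15.49 + 0.15×4 + 0.06×5.5) = 15.49 / 16.42 = 0.943
- a2 = 0.32: 14.28 / (14.28 + 0.15×4 + 0.17×5.5) = 14.28 / 15.815 = 0.903

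Share captured = S / (S + U), with S = 19(1 − a2) + 8k(a2 − a1) and U = k[4a1 + 5.5(a2 − a1)]. For k = 2 and a2 = 0.21: 15.97 / (15.97 + 1.86) = 0.896.

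| Share of visits captured | k = 2 | k = 3 | k = 4 |
|---|---|---|---|
| A, 21% lost | 69.5% | 61.0% | 54.7% |
| B, 21% lost | 89.6% | 85.5% | 82.0% |
| A, 32% lost | 62.4% | 54.6% | 49.3% |
| B, 32% lost | 83.6% | 78.7% | 74.9% |

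Actual loss will mix the two cases, so the answer lies between the A and B rows for a given loss and k.

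**The case against.** The strongest reply is that this is a tertiary, exploratory outcome in a 50-dyad feasibility pilot, that the interview was chosen because it had been sensitive to change in an earlier cancer trial, and that charts at two health systems miss care elsewhere even for fully retained patients. All of that stands. It sets the priority and argues against replacing the interview. It does not remove the gap.

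Two other replies are weaker. The planned multiple imputation is general and has no rule for use before death. Serious adverse event records may hold some admissions, but they depend on notification and are not named as a source for Aim 3.

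A reader might infer more than the documents support:
- *That the heaviest-use weeks are the ones missed.* The documents give no use rate by time to death. Some removals (choice, unanswered calls, caregiver loss) need not mark heavy users, and patients entering hospice may continue. The link to illness is plausible, not shown.
- *That only Case A applies.* It keeps patients who died at risk to week 19, so both cases must be shown.
- *That the arm contrast is distorted or reversed.* Suppose 10% of one arm and 30% of the other are lost, half before the 2-week visit, with k = 3 and no other arm difference. Under Case A the full-count ratio is (0.9 + 0.3) / (0.7 + 0.9) = 0.75, the raw interview ratio is 18.3 / 16.9 = 1.08, and with an offset it is (18.3 / 17.5) / (16.9 / 14.5) = 0.90. The whole effect comes from the assumed imbalance, 2.5 against 7.5 patients at 25 per arm. Nothing in the documents supports that imbalance.
- *That hospital admissions are an Aim 3 outcome, or that charts are reviewed for cancer information alone.* Admissions are not among the named domains. The Table 2 entry is an open list of examples, and the data collection sheets in Appendix S are not reproduced.

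**Conclusion.** The point holds as a limited one. The plan asks for whole-period patient service use and names a single source that can stop early, while charts for the same patients are already scheduled for review at the same three times. With 15% then 21% lost, interviews cover between about 82% and 94% of patient time at risk (75% to 90% with 32% lost). With a 2- to 4-fold use rate in lost patients, the captured share of visits is about 70% to 55% if they stay at risk to 3 months and 90% to 82% if risk ends midway (62% to 49% and 84% to 75% with 32% lost).

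These ranges rest on target-date timing, no interview after loss, retention borrowed partly from another population, and an assumed rate ratio. They show incomplete counts. They do not show a biased arm comparison, which would need loss to differ by arm. It is a low-priority improvement to an exploratory aim that feeds the later trial, and primary and secondary conclusions are untouched.

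**What to change.** At the chart reviews already scheduled, also record dates of patient ER visits (and of admissions, if they are among the five domains) from randomisation to the 3-month date or death. Do this for every randomised patient whose authorization still applies, including those who died or stopped interviews.

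Keep the interview report as the planned Aim 3 source. Add to Aim 3 a chart-based analysis of patient ER use at the two health systems in all randomised patients, with time at risk to death or 3 months. Its purpose is to show whether the arm contrast depends on who could be interviewed. Caregiver use and care elsewhere remain with the interview.

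Cost: a few fields on the chart-review form, after checking whether Appendix S already has them; a check that the authorization covers them and of what it allows after withdrawal; and a sentence or two in section 11.0. Participants carry no extra burden. The remaining weakness is that chart counts omit visits outside the two systems, so they supplement the interview and do not replace it.
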